1.3 SCHEDULE OF ACTIVITIES (SOA)

2 INTRODUCTION

2.1 STUDY RATIONALE

Early detection of foot ulcers in diabetics can allow timely intervention to prevent severe disease and amputation. New technology to allow home monitoring of foot temperature has been developed and demonstrated to be effective to detect early foot changes. Knowledge of uptake and adherence of this device is needed to determine if this technology could be effectively deployed to our patient population to improve outcomes.

2.2 BACKGROUND

A.1 Diabetic Foot Ulcers represent a major public health crisis, resulting in large morbidity for individuals and extracts large resources from health care systems.

Diabetic foot ulcers (DFU) remain a prevalent and highly morbid complication of diabetes. The effects of DFU and amputation on the individual are substantial with declines in well-being, economic instability, and depression. The impact of DFU's on U.S. health care costs is large and have been estimated to be 9-13 billion dollars annually. Furthermore, the prevalence of DFU differs by race and ethnicity. Non-Hispanic Black (NHB) or Hispanic/Latino (H/L) persons have a higher prevalence of diabetes, and amputations than persons who are non-Hispanic white (NHW). This crisis of DFU is seen every day on the inpatient service at Montefiore Medical Center (MMC), which offers health care to one of the most diverse and poorest communities in the U.S.

A.2 Need for technologic innovations for foot monitoring that is feasible, sustainable, and robust

The mechanism of the development of neuropathic foot ulcerations involves repetitive trauma at pressure point on the sole of the foot over several days. Due to the neuropathy, patients do not detect subtle inflammatory changes in the foot such as pain, erythema, swelling which are harbingers of ulceration. It has been shown that an increase in foot temperature as defined as increase by 2.2°C or 4°F, can detect early inflammatory changes, and if offloading is instituted, healing can occur to prevent ulceration. We will test the feasibility of a home foot temperature monitoring system in our MMC patients with Type 1 or Type 2 diabetes. Study subjects will stand on the mat daily, the temperatures are transmitted and if there are significant changes, the provider is alerted. There is a growing literature that demonstrating that these devices allow prompt detection and treatment to prevent severe DFU and need for a lower extremity amputation (LEA). Using FDA approved technology from Podometrics (Somerville, Massachusetts), study subjects can use a telemedicine foot temperature monitoring mat to monitor the bottoms of their feet daily. This requires them to step on the mat, and the data will be automatically transmitted to Podometrics for analysis. The mat embeds cellular technology for the transmission to occur. The use of this device has shown to (1) reduce the rate of hospitalization (RRR 0.52), (2) lower extremity amputation (RRR 0.71), (3) reduce the number of outpatient visits and (4) reduce the development of severe wounds (RRR 0.91). Podometrics is an FDA 510 (k) cleared medical device for evaluation of the temperature over the soles of the feet for signs of inflammation.

Podometrics provides the mat, wireless transmission of data, patient/subject training in the use of the mat, and reinforcement in the case of non-adherence. The Podometrics team monitors the data and when there is an increase in 2.2°C over two consecutive uses between and of six contralaterally matched locations, the study team is contacted. Accuracy of this approach predicts 97% of plantar DFU in patient in diabetic foot remission.

3 STUDY DESIGN

3.1 OVERALL DESIGN

This is a longitudinal cohort study. We will test the uptake and adherence of a novel foot monitoring device and collect data regarding the occurrence and severity of DFU and use of health care resources to inform future larger clinical trials.

4 STUDY POPULATION

4.1 INCLUSION CRITERIA

1. Type 1 or Type 2 diabetes mellitus
2. Prior treatment of DFU within 24 months
3. Subject had at least one outpatient follow up with a provider after treatment for DFU
4. No active ulcer at time of enrollment
5. Male or female, aged <18-75 yrs>
6. Presence of neuropathy
7. Ambulatory
8. Provision of signed and dated informed consent form
9. Stated willingness to adhere with all study procedures and availability to participate for the duration of the study

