1 PROTOCOL SUMMARY

1.1 SYNOPSIS

Title: Adherence to novel foot mat technology for early detection of DFU.

Study Description:

Innovations toward the prevention of DFU are needed. Early detection of changes in the foot that predict the development of DFU could allow timely intervention to prevent the limb damage that occurs with advanced DFU.

Studies have demonstrated that increased temperature in the foot presage the development of DFU. Temperature changes can accurately be detected by home monitoring devices and predict impending ulceration. Here we will test the uptake of novel foot temperature monitoring technology for a future intervention study to determine if a home monitoring device could prevent the occurrence of severe DFU for our patients at MMC.

We will conduct a longitudinal study to determine the adherence to an FDA cleared device, Podimetrics, which has been tested in other populations and shown to 1) decrease the risk of severe DFU, and 2) decrease the utilization of health care resources in high risk patients with a history of DFU. For this study, we will identify and enroll patients who are high risk for DFU. They will be identified from the EMR. After informed consent, study subjects will receive the foot mat and obtain training remotely from Podimetrics, which provides a standardized training program. Study subjects briefly stand on the mat daily, and the temperature data automatically is sent for analysis to Podimetrics to interpret the information. The study subjects will be evaluated over a six-month period to measure their daily use of the technology. Secondary outcomes of this study include the occurrence of DFU and use of health care resources. Study subjects will be contacted every month by the study team to assess foot health. Study subjects will be instructed to contact the study team during the study period to inquire if they develop any changes in the foot such as the diagnosis of DFU or require a foot cast for offloading or have any concerns about their feet.

If patients have an increase in temperature, the study team will be contacted by Podimetrics. After a review of symptoms, a standard care protocol will be executed: offloading (decrease in weight bearing) will be recommended. In one study 68% of cases

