4.2 EXCLUSION CRITERIA

1. Active DFU
2. Unable to comply with study requirements.
3. Prior AKA or BKA

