6 STATISTICAL CONSIDERATIONS

This study is primary to assess adherence to the monitoring device. It is not powered to assess clinical outcomes or use of health care resources.

- We will plan for 20 subjects to complete the study, and plan to enroll up to 40 patients to account for drop out or exclusion.
- Measurement of adherence (primary outcome)
 - Adherence is defined as > 3 days/week during the six month period
 - We will record the number of re-engagement calls per participant over the 6 month study period
 - We will record the number lost to follow up, unable to comply, or are hospitalized (4.2, 4.3)
- Measurement of secondary outcomes
 - Number of subjects who develop a DFU over the course of the study
 - Utilization of health care resource use (total number of: ER visits, outpatient visits) over the course of the study

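### Inclusion 9 and an undefined compliance exclusion overlap with the adherence outcome, and no screening count is planned, so the estimate covers consenting patients in follow-up rather than the site population

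*Combined protocol and SAP*

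**What the plan says.** Section 6 sets the primary outcome: "Adherence is defined as > 3 days/week during the six month period". Section 2.1 says what it is for: "Knowledge of uptake and adherence of this device is needed to determine if this technology could be effectively deployed to our patient population". The synopsis and section 3.1 give a narrower purpose: to "test the uptake of novel foot temperature monitoring technology for a future intervention study", and "to inform future larger clinical trials".

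Three entry criteria bear on adherence:

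- Section 4.1 item 9 requires "Stated willingness to adhere with all study procedures and availability to participate for the duration of the study".
- Section 4.1 item 3 requires "Subject had at least one outpatient follow up with a provider after treatment for DFU".
- Section 4.2 item 2 excludes patients "Unable to comply with study requirements". The term is not defined.

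After entry, section 7.2 lets the investigator withdraw a participant for significant non-compliance, or because an exclusion criterion is newly met or newly recognised. A participant who withdraws or is lost is replaced. Under measurement of the primary outcome, section 6 says that the number unable to comply will be recorded, with a cross-reference to 4.2. It does not say whether they stay in the adherence denominator. Section 6 plans for 20 completers and enrolment of up to 40.

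The schema in section 1.2 describes recruitment through the EMR, email, phone and clinics. The text provided has no plan to count or report patients approached, ineligible by criterion, or declining.

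**The concern.** In most trials a willingness criterion and a compliance exclusion are routine wording. Here the main continuing task for a participant is standing on the mat each day. The other tasks are one enrolment visit, training, monthly calls and returning the mat. A promise to follow all procedures is therefore largely a promise about the endpoint, and an undefined inability to comply can be read as a forecast of the endpoint.

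The exclusion matters more than the inclusion because it can act twice. At screening it can keep out someone thought unlikely to use the mat. During follow-up, through section 7.2, it can remove someone who is not using it, and a replacement is then enrolled.

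At stake is how far the result carries. If patients who doubt they would use the mat leave no trace, a reader cannot tell how large the unobserved group is, and the adherence figure may be taken to apply to all the site's patients with a prior DFU. A later trial that recruited more broadly would inherit the same optimism.

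**Working it through.** **The plan's own figures.** The documents give no dropout rate, precision target or power, so 20 and 40 cannot be derived from stated inputs. Working backwards with enrolled = completers / (1 − loss), 20 / (1 − 0.50) = 40. The maximum enrolment thus allows for 50% loss or exclusion, a rate the plan does not state.

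**Sampling error for scale.** Assume 14 of 20 completers are adherent. That is 70%, with an exact 95% interval of 45.7% to 88.1% and a half-width of (88.1 − 45.7) / 2 = 21.2 points.

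**Selection before entry.** Let A be adherence among those enrolled, e the share of the target population who pass the criteria and consent, and r the adherence of everyone else relative to A. Then

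population adherence = e × A + (1 − e) × r × A.

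All three inputs are assumptions. With A = 70%:

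| e | r = 0 | r = 0.5 | r = 1 | largest gap, A × (1 − e) |
|---|---|---|---|---|
| 0.9 | 63% | 66.5% | 70% | 7 points |
| 0.7 | 49% | 59.5% | 70% | 21 points |
| 0.5 | 35% | 52.5% | 70% | 35 points |

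At e = 0.9 the gap is small beside the sampling half-width. At e = 0.7 the largest gap about equals it, and at e = 0.5 it exceeds it. A screening log would supply e. With e known, the population figure can be bounded, though not identified, because r stays unobserved.

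**Selection after entry.** If 40 are enrolled, 20 complete and 14 completers are adherent, adherence is 14/20 = 70% of completers. If none of the 20 lost was adherent, it is 14/40 = 35% of those enrolled (exact 95% interval 20.6% to 51.7%). This loss has many possible causes, and only part could come through 4.2 item 2. It shows why the denominator must be stated when non-compliance is itself a ground for removal.

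**Aim set against data.** Sections 1.1, 2.1 and 3.1 name uptake. Uptake needs a numerator (enrolled) and a denominator (eligible and approached). The plan collects the first only. The section 6 count of those unable to comply points to 4.2, but the text does not say whether it covers screening, and it would not include patients who decline.

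**The case against.** The strongest reply is that the entry criteria select on declared intention and likely predictors, and that this differs from selecting on the outcome. There is no run-in, no trial use of the mat and no adherence threshold at entry. Item 3 asks for one prior visit. Section 1.2 expects lapses after enrolment, with reinforcement when four days are missed, and section 6 counts re-engagement calls. Signed consent (item 8) would select willing patients even without item 9. The mat can only work for someone who agrees to stand on it, so adherence among willing patients is a proper part of deployability. It also fits the stated aim of informing future trials, provided that they use similar criteria.

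This all stands, and it rules out two stronger readings. A reader might infer that the study cannot answer whether the mat is "needed to determine if this technology could be effectively deployed to our patient population". The documents do not support that: the question has two parts, uptake and adherence among those who accept, and the plan measures the second. A reader might also infer a definite shortfall, for example 0.70 × 0.80 = 56% or 0.70 × 0.60 = 42% if 20% or 40% of patients are filtered out. Those results require every filtered patient to be non-adherent and rest on assumed inputs throughout.

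The reply does not dispose of the undefined wording of 4.2 item 2, its reach after entry through section 7.2, or the missing uptake denominator. The wording gives staff no explicit instruction to predict mat use, but nothing in it prevents that reading.

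**Conclusion.** The concern holds in a limited form. Item 9, and more so 4.2 item 2, overlap with the primary outcome. Through section 7.2 the undefined exclusion can also remove non-adherent participants, who are then replaced. With no screening count planned in the text provided, the estimate applies to consenting, willing patients who have attended outpatient follow-up after DFU.

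It probably overstates adherence in the wider population of section 2.1. That direction assumes that patients who are screened out or decline would use the mat no more than those enrolled (r ≤ 1), which is plausible but untested. The size cannot be computed from the documents. On an assumed 70% among those enrolled, the gap runs from nil to 7 points if 90% enter and from nil to 35 points if half enter. The study remains useful for its narrower purpose. The point warrants a change because the remedy is cheap and supplies information that the plan's own uptake aim needs.

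**What to change.** 1. Limit 4.2 item 2 to inability to stand on or operate the mat. State in 4.1 item 9 and 4.2 item 2 that the expected or observed frequency of mat use is not a reason for ineligibility or for removal from the adherence denominator. The statement on 4.2 item 2 carries most of the benefit; for item 9 it adds little beyond what consent already does. Section 6 should say the same of the denominator, so that a participant withdrawn under section 7.2 for non-compliance is still counted in the primary outcome.
2. Log and report the numbers identified, approached, ineligible by each criterion (4.1 items 3 and 9, and 4.2 item 2 in particular), declining and enrolled. Report uptake alongside adherence.
3. Keep item 3 if it is wanted, and limit the conclusion to consenting patients in outpatient follow-up after DFU.

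The cost is a few sentences in sections 4 and 6 and a small logging burden, with no added visits or tests. Observed adherence may come out lower.

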4.2 EXCLUSION CRITERIA

1. Active DFU
2. Unable to comply with study requirements.
3. Prior AKA or BKA

4.3 A STUDY SUBJECT DEVELOPS A DFU REQUIRING HOSPITALIZATION

1. Data is censored from the date of hospital admission.

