resolved via offloading alone without an outpatient visit. Should the inflammation persist (increased temperature), despite off loading, an examination would be necessary to identify and resolve its cause. In this case the patient will be instructed to follow up with their physician.

Objectives:

Primary Objective:

1. Determine the adherence to the foot monitoring device over six months.

Secondary Objectives:

1. Determine the prevalence of ulcers as detected by the device.
2. Determine the use of the health care system.

Endpoints:

Study Population:

Adherence to daily monitoring, development of ulcers

The study cohort are derived from patients who are at highest risk to develop a DFU. They are patients who had a prior DFU within 24 months. Other criteria include: 1. have no active ulcer at the time of enrollment, 2. Presence of neuropathy, 3. ambulatory, and 4. provide informed consent.

Description of Sites/Facilities

The study will be conducted at one site Albert Einstein College of Medicine (AECOM) and its affiliated Montefiore Medical Center.

Enrolling Participants:

Description of Study:

Subjects will undergo observation for 6 months

Study Duration:

12 months

Participant Duration:

6 months

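### Censoring of unstated scope at a DFU admission, with utilization counted only as a raw ER and outpatient total, biases the descriptive utilization estimate downward

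*Combined protocol and SAP*

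**What the plan says.** - **Censoring rule.** Section 4.3, headed "A STUDY SUBJECT DEVELOPS A DFU REQUIRING HOSPITALIZATION", has one line: "Data is censored from the date of hospital admission". It names no type of data and exempts no outcome.
- **Utilization outcome.** Section 6 defines it as "Utilization of health care resource use (total number of: ER visits, outpatient visits) over the course of the study". Inpatient admissions are not listed, and there is no person-time denominator.
- **DFU outcome.** Section 6 also lists "Number of subjects who develop a DFU over the course of the study".
- **Where hospitalization appears.** Under the adherence measurement, Section 6 says "We will record the number lost to follow up, unable to comply, or are hospitalized (4.2, 4.3"; the closing cross-reference is to the exclusion criteria and the censoring rule.
- **Objective and purpose.** The second secondary objective in the synopsis is "Determine the use of the health care system", with no restriction to ambulatory care. Section 3.1 says the study will "collect data regarding the occurrence and severity of DFU and use of health care resources to inform future larger clinical trials".
- **Follow-up.** Observation is for six months (synopsis). All participants are called monthly about ulcers and health care use (Section 1.2, part A, item 9). Section 7.2 allows withdrawal of a participant who newly meets an exclusion criterion, and active DFU is one (Section 4.2).
- **Power.** Section 6 states that the study is not powered for clinical outcomes or resource use.

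**The concern.** The event that ends data collection under 4.3 is a severe form of one secondary outcome (DFU), and it generates much of what the other (health care use) is meant to measure. Censoring of this kind is informative: the time lost is not like the time kept. The definition in Section 6 then leaves out the admission as well, although the objective refers to the health care system as a whole and Section 2.2 cites evidence that the device can "reduce the rate of hospitalization (RRR 0.52" in parentheses there).

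A raw total adds a second problem. It falls when follow-up is shorter, whatever the reason, so a cohort with more severe disease or more withdrawals can appear to use less care. At stake is a planning figure: someone sizing a later trial from this total would start from a number that is too low.

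**Working it through.** **The plan's own figure.** There is none to reproduce. The documents give no visit rate, admission rate or dropout rate, and the 20 completers and up to 40 enrolled carry no derivation. Only n = 20 and the six months below come from the documents; everything else is assumed.

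**Step 1. What is counted after a DFU admission, read literally.**
- The DFU: counted, because 4.3 applies only once a DFU has been identified.
- The admission: recorded as a hospitalized participant under adherence; 0 in the utilization outcome.
- An ER visit on the day of admission: dropped, because censoring runs from that date.
- Later ER and outpatient visits: dropped.
- Admissions for other causes: not censored by 4.3, but not in the utilization definition either.

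**Step 2. Follow-up lost.** If a share h is admitted at month m, the fraction of planned person-months lost is h × (6 − m)/6, the same for 20 or 40 participants.
- h = 5%, m = 5: 0.05 × 1/6 = 0.8%
- h = 10%, m = 3: 0.10 × 3/6 = 5.0%
- h = 20%, m = 1: 0.20 × 5/6 = 16.7%

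**Step 3. Effect on the ER plus outpatient total.** Take n = 20, k = 20h admitted at month 3, 1 visit per month before admission and for everyone else, and r visits per month after admission.
- Full total = (20 − k) × 6 + k × (3 + 3r)
- Censored total = (20 − k) × 6 + k × 3
- Understatement = 1 − censored/full

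| Admitted | Censored total | Full total, r = 1 / 2 / 3 | Understated by |
|---|---|---|---|
| 5% (k = 1) | 117 | 120 / 123 / 126 | 2.5% / 4.9% / 7.1% |
| 10% (k = 2) | 114 | 120 / 126 / 132 | 5.0% / 9.5% / 13.6% |
| 20% (k = 4) | 108 | 120 / 132 / 144 | 10.0% / 18.2% / 25.0% |

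The utilization outcome also counts 0 of the 1, 2 or 4 admissions.

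**Step 4. Would a rate alone repair it?** Only in part. With 10% admitted and r = 3, the censored data give 114 visits over 114 person-months, or 1.00 per month. Full follow-up gives 132/120 = 1.10. A person-month denominator removes the effect of shorter follow-up, but not that of losing the months with heavier use. For that, collection has to continue.

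**Step 5. Is it likely to arise?** The chance of at least one DFU admission is 1 − (1 − p)^n. For an assumed six-month risk p of 5%, 10% or 20%, it is 64%, 88% or 99% with n = 20, and 87%, 99% or over 99% with n = 40.

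**The case against.** The best defence is that 4.3 was meant for adherence. A participant in hospital cannot step on a mat at home, Section 6 cites 4.3 only under the adherence measurement, and nothing in Section 1.2 stops the monthly calls at an admission. This stands in part: the all-data reading is the literal one, not a proven intention. But a rule with no stated scope can be applied literally, and the utilization definition omits admissions under either reading.

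The study is also a single cohort with adherence as primary and no test or decision resting on utilization. With 20 completers any such estimate is imprecise: 2 of 20 has an exact 95% interval of about 1% to 32%. This lowers the priority of the point. It does not justify a definition that errs in a known direction, since description for later planning is the stated use.

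Four stronger readings are tempting, and the documents do not support them.

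- *Hospitalization will have no estimate.* Section 6 records the number hospitalized, which gives a proportion. What is lost is its place in utilization, and any repeat DFU admissions and visits after the first.
- *The ulcer that leads to admission disappears.* The rule presupposes a DFU, which meets the Section 6 DFU outcome. Saying so explicitly would remove doubt about one first recognised at admission.
- *Utilization must be lowest in the sickest.* Their visits before admission count and may be many. Their record is truncated, not necessarily lowest.
- *The total could swing by more than half.* Suppose 20 completers and 20 early leavers, at an assumed 0.5 visits per month. The total is 0.5 × (120 + 20) = 70 if leavers stay 1 month and 0.5 × (120 + 100) = 110 if they stay 5, a ratio of 1.57. That shows how a raw total depends on general dropout of half the enrolled. It does not measure the effect of 4.3, and it presumes that leavers' visits are pooled with completers', which the plan does not say.

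Nor can it be said that ulcer severity goes uncollected. Section 3.1 says that it will be collected, and the case report form is not among the documents.

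**Conclusion.** The concern holds in limited form. As written, the plan cuts off the secondary utilization outcome at a DFU admission, leaves admissions out of it, and reports a total that falls with shorter follow-up. For the total, the downward direction does not depend on any assumed rate, because dropped visits and uncounted admissions can only reduce it. The size does: about 2.5% to 25% under the scenario shown, with admission risk, timing and visit rates all assumed. If 4.3 was intended for mat-use data only, the truncation goes away, but the missing admissions and the missing denominator remain.

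This should be fixed, but it is not critical. It affects a descriptive secondary estimate in a study that disclaims power for it. A reader might infer that the primary adherence result is compromised by the utilization definition; it does not depend on that definition.

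**What to change.** 1. In 4.3, state that censoring applies to mat-use (adherence) data only.
2. State that the DFU and the admission that trigger the rule are both counted as outcome events.
3. After an admission, continue the monthly calls already planned in Section 1.2, with EMR capture, to month 6.
4. Add inpatient admissions to the Section 6 utilization list.
5. Report utilization as a rate per person-month observed, with a 95% CI that treats the participant as the unit because visits cluster within people, beside the total.

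Items 3 and 5 belong together: Step 4 of the working shows that the rate alone leaves part of the bias.

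The cost is wording in two sections, a few case report form fields, continued calls for the few participants admitted, and use of the EMR beyond the identification and baseline extraction now described. The change is best made before data collection, since visits not recorded at the time may be hard to recover. Amputation, inpatient days and a flag for visits prompted by a mat alert would be useful, but they are optional additions and do not correct an error.
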